4.2.2 Handling of Missing Safety Data

In general, missing clinical laboratory data, vital signs, and ECG data will not be imputed. Adverse event imputations for missing severity or relationship are described in Section 9.1. Unknown or partial medication and AE date imputations are given below and are to be used only for the assessment of prior/concomitant status for medications and treatment-emergent status for AEs.

4.2.3 Handling of Partial and Missing Dates for Adverse Events, Prior / Concomitant Medications, and Last Dose of Study Drug

For AEs with partial or missing onset or stop dates:

- AE stop date will be imputed first as:
 - o If the stop date is completely missing, assume it is ongoing (no imputation);
 - o For a partial AE stop date:
 - the day is missing, then take the last day of the month
 - both day and month are missing, then take December 31st.
 - o If the imputed AE stop date is after the End of the Study date, then the stop date will be set to the End of the Study date.
- Then AE onset date will be imputed as:
 - o If the onset date is completely missing, the first dose date;
 - o For a partial AE onset date:
 - Day is missing:
 - Partial date < the first dose date: last day of the month
 - Partial date = the first dose date: the first dose date
 - Partial date > the first dose date: first day of the month
 - Both day and month are missing, ie, only the year is available:
 - Partial date < the first dose date: 31st December
 - Partial date = the first dose date: the first dose date
 - Partial date > the first dose date: 1st January.
 - o If the imputed AE onset date is after the AE stop date/imputed AE stop date, then the onset date will be set to the AE stop date/imputed AE stop date.

In the event that a partial date (month/year or year) for concomitant medication is available, concomitant medication start and stop dates will be imputed as:

• When both month and year are available – the first day of the month will be used for the start date, and the last day of the month will be used for the stop date.

Protocol Reference: CLR 18 06

• When only year is available – 01 January will be used for the start date and 31 December will be used for the stop date.

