9.1 Adverse Events

All AEs recorded on the eCRF will be coded using the MedDRA dictionary (version 23.0 or a later version if updated during the study) and classified as either pre-treatment AEs or TEAEs for Part 1 or Part 2 of the study as follows:

- Pre-treatment AEs are events that start prior to the start of the Treatment Period.
- TEAEs are either events with start date / time on or after the start of the Treatment Period, or events with start date / time prior to the start of the Treatment Period whose severity worsens on or after the start of the Treatment Period.
- TEAEs for Part 1 of the study are all TEAEs for those subjects not participating in Part 2 of the study and those TEAEs with start date / time before the date of first dose for Part 2 of the study for subjects participating in Part 2 of the study.
- TEAEs for Part 2 of the study are those TEAEs with start date / time on or after the date of first dose for Part 2 of the study.
- Serious TEAEs will be defined as TEAEs regarded by the investigator as Serious = "Yes".
- The relationship between TEAE and study medication is assessed as certainly, probably, possibly, unlikely or unrelated. A study treatment related TEAE will be defined as a TEAE considered by the investigator as certainly, probably, or possibly related to study medication or with missing relationship to study medication.
- Assessment of AE severity will be characterized as mild, moderate, severe, life-threatening and death.
- TEAEs leading to discontinuation of study are defined as TEAEs where "Did AE caused subject to discontinue from the study?" is indicated as "Yes".
- TEAEs leading to discontinuation of study treatment are defined as TEAEs where "Action taken with Study Medication" is indicated as "Drug Discontinued".

AEs will be summarized by default descriptive summary statistics for categorical variables by treatment group and overall, for Parts 1 and 2 of the study separately, using the Safety Analysis Set, Part 1 and Safety Analysis Set, Part 2 respectively, as follows:

• An overview of TEAEs including the number and percentage of subjects with at least one of each mentioned TEAE type:

- Any TEAE
 - Leading to discontinuation of study treatment
 - Leading to death
 - Severity: mild
 - Severity: moderate
 - Severity: severe
 - Severity: life-threatening
 - Severity: death
- Any study treatment-related TEAE
 - Leading to discontinuation of study treatment
 - Leading to death
- Any serious TEAE

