 - Leading to discontinuation of study treatment
 - Leading to death
- Any serious study treatment-related TEAE
 - Leading to discontinuation of study treatment
 - Leading to death
- The number and percentage of subjects reporting each TEAE and the count of number of events will be summarized by SOC and PT for the following types of TEAEs:
 - TEAEs
 - TEAEs Leading to Discontinuation of Study Treatment
 - TEAEs Leading to Death
 - TEAEs by Maximum Severity
 - TEAEs by Relationship to Treatment
 - TEAEs by Relationship and Maximum Severity
 - Study Treatment-Related TEAEs
 - Study Treatment-Related TEAEs Leading to Discontinuation of Study Treatment
 - Study Treatment-Related TEAEs Leading to Death

- Serious TEAEs
- Serious TEAEs Leading to Discontinuation of Study Treatment
- Serious TEAEs Leading to Death
- Study Treatment-Related Serious TEAEs
- Study Treatment-Related Serious TEAEs Leading to Discontinuation of Study Treatment
- Study Treatment Related Serious TEAEs Leading to Death
- The number and percentage of subjects who died will be summarized
- The number and percentage of subjects reporting each TEAE and the number of events will be summarized by PT

AEs for Part 1 of the study will be summarized by default descriptive summary statistics for categorical variables by formulation category and overall, using the Safety Analysis Set, Part 1, as follows:

- An overview of TEAEs including the number and percentage of subjects with at least one of each mentioned TEAE type above.
- The number and percentage of subjects reporting each TEAE and the number of events will be summarized by SOC and PT.
- The number and percentage of subjects reporting each TEAE and the count of number of events will be summarized by PT.

In the above summaries, subjects with more than one TEAE within a particular SOC are counted only once for that SOC. Similarly, subjects with more than one TEAE within a particular PT are counted only once for that PT.

For summaries by maximum severity, subjects with multiple TEAEs within a particular SOC or PT will be counted under the category of their most severe TEAE within that SOC or PT. TEAEs with missing severity will be included in the overall count of subjects with TEAEs, but will not be included in the counts of subjects with TEAEs within a SOC or PT.

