12.2 General rules for Statistical Reporting

In general, statistical reporting and analyses will be created separately for Part 1 and Part 2.

The default summary statistics for quantitative variables will be the number of observations (n), mean, SD, median, minimum (min) and maximum (max), for those subjects with data. In addition, geometric mean and CV% of geometric mean will be reported for PK parameters.

All summary statistics will be rounded (using the more decimal place than the raw value, except for the SD and SE values that will be presented to 2 more decimal places than the raw value, and minimum and maximum values that will be presented with the same decimal precision as the raw value. All summary statistics for PK data will be rounded (using the analysis) and presented to 3 significant figures, except for the geometric CV values that will be presented to 1 decimal place.

For qualitative variables, the number (n) and percentage (%) of subjects with non-missing data per category will be the default summary presentation, and where appropriate and present, the number of missing values as a "Missing" category. The number of subjects in the analysis population will be used as denominator for percentages calculation, unless stated otherwise in Tables, Figures and Listings (TFL) mock shell(s).

All statistical comparisons and tests will be performed at the significance level unless specifically stated otherwise.

All central laboratory test results will be provided in International System of Units (SI) and all local laboratory test results will be provided in conventional units.

For the TFL, the results will be summarized or presented in Refer to Appendix of the TLF mock shells for the SI unit corresponding to each laboratory test and the precision level in which each laboratory test is reported by the central laboratory.

Specifications for table, figures and data listing formats can be found in the TFL shells specifications for this study. Please refer to "2. General Format Guidelines" section within TFL shells for more details on presentation of results.

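### SAP 4.2.2 promises an imputation for missing adverse event severity that SAP 9.1 does not give; 9.1 leaves ungraded events out of the SOC and PT rows of the maximum-severity tables, which can then undercount

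*SAP*

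**What the plan says.** SAP 4.2.2 (Handling of Missing Safety Data) states: "Adverse event imputations for missing severity or relationship are described in Section 9.1".

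SAP 9.1 (Adverse Events) treats the two items differently.

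- **Relationship.** The definition of a treatment-related TEAE takes in events that are "possibly related to study medication or with missing relationship to study medication". A missing relationship thus counts as related.
- **Severity grades.** "Assessment of AE severity will be characterized as mild, moderate, severe, life-threatening and death". That is five categories, none of them for a missing grade.
- **Missing severity.** The paragraph that holds the rule opens: "For summaries by maximum severity, subjects with multiple TEAEs within a particular SOC or PT will be counted under the category of their most severe" event in that SOC or PT. It then says that "TEAEs with missing severity will be included in the overall count of subjects with TEAEs, but will not be included in the counts", meaning the counts of subjects at SOC or PT level.

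Two other places bear on the point. SAP 12.2 sets the default display for qualitative variables, which includes, where appropriate and present, "the number of missing values as a 'Missing' category". Protocol 9.8 says that missing safety data are in general neither imputed nor substituted, and refers to the SAP for further detail.

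**The concern.** The two SAP sections do not agree. One announces an imputation for severity; the other has an exclusion. A programmer who follows 4.2.2 looks for a rule that does not exist, and one who follows 9.1 removes subjects from rows.

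The exclusion works in one direction. It can take a subject out of a SOC or PT row but can never add one. By its placement it applies to two planned outputs: TEAEs by maximum severity, and TEAEs by relationship and maximum severity. In these the SOC and PT counts may fall short of the overall row of the same table and of the corresponding rows in the plain SOC/PT table. A reader would see totals that do not reconcile and would not be told why. These tables show how severe each type of reaction was, so a subject who is silently absent matters most in a rare term.

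**Working it through.** The documents state no figure on this point, so there is none to reproduce. The check has two parts.

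**1. The rule applied to a small example.** Take five subjects with the same PT:

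| Subject | Grades recorded in the PT | Row under SAP 9.1 |
|---|---|---|
| 1 | mild | mild |
| 2 | moderate | moderate |
| 3 | severe | severe |
| 4 | missing | none |
| 5 | missing, mild | mild |

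The overall count is 5, but the PT severity rows hold 4. Subject 4 is lost. Subject 5 stays in at the known grade, so for that subject the risk is a grade that is too low, not a lost count. With a 'Missing' row all five are counted.

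**2. Expected size.** Subjects lost per PT row per arm = n × p × m^k, where:

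- n = 506 / 3 = 168.7 per arm (506 planned, randomized 1:1:1, from the protocol);
- p = true proportion of subjects with the PT (assumed 5%, 10%, 20%);
- m = chance that an event has no severity grade, taken as independent between events (assumed 0%, 1%, 5%);
- k = events per subject in that PT (assumed 1 or 2).

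The true counts n × p are 168.7 × 0.05 = 8.4, 168.7 × 0.10 = 16.9 and 168.7 × 0.20 = 33.7.

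| p | m = 0 | m = 1%, k = 1 | m = 5%, k = 1 | m = 5%, k = 2 |
|---|---|---|---|---|
| 5% | 0 | 0.08 | 0.42 | 0.02 |
| 10% | 0 | 0.17 | 0.84 | 0.04 |
| 20% | 0 | 0.34 | 1.69 | 0.08 |

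For example, 33.7 × 0.01 = 0.34 and 33.7 × 0.05 = 1.69. With two events per subject the loss stays below 0.1 subject throughout.

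For a rare PT with 3 subjects and m = 1%, the expected loss is 3 × 0.01 = 0.03 subjects. If a loss does occur there, it removes 1/3 of the count.

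**The case against.** The best defence is that little can be lost and that not imputing follows the protocol.

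- **Missing grades should be rare.** Protocol 8.4 requires severity for each adverse event. Protocol 10.4 provides validation rules, queries and a lock only once the data are validated. Protocol 5.4.3 breaks the code after cleaning and lock. This stands, and it is why the size is probably small.
- **The events appear elsewhere.** SAP 9.1 also plans plain SOC/PT tables, several restricted SOC/PT tables, a PT-only table and a listing of all adverse event data. This stands too. A reader might infer that the plan understates event rates by organ class or preferred term in general. The text does not support that: the exclusion sits inside the paragraph on maximum severity.
- **Protocol 9.8 favours no imputation.** This stands as far as the grade is concerned. It explains why 9.1 imputes nothing and suggests that the stray wording is in 4.2.2. It does not justify leaving the subject out of the row, because an ungraded event can be shown as ungraded.
- **SAP 12.2 already provides for a missing category.** Only in part: the specific sentence in 9.1 overrides that default at SOC and PT level.

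A reader might also infer, from the cautious handling of a missing relationship, that a missing grade ought to be counted as severe. The documents do not support this. It would run against the general principle in Protocol 9.8 and assign a grade that no investigator gave.

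**Conclusion.** The inconsistency between SAP 4.2.2 and 9.1 is plain on the text. The undercount is conditional: it arises only when a subject's sole TEAE in a SOC or PT lacks a grade. A reader might infer that the severity tables will undercount; the documents support only that they can, since they give no rate of missing severity and do not say which events would lack a grade.

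Under the stated assumptions a PT row loses a fraction of a subject per arm at 1% missing. At 5% missing and 20% incidence it loses up to about 1.7, and with complete grading nothing. The incidence, the missing rate and the number of events per subject are all assumed.

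This is a minor reporting point. It does not touch the primary analysis, the plain adverse event tables or the listing, and it is worth correcting because the correction is almost free.

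**What to change.** - **SAP 9.1:** keep TEAEs with missing severity in all SOC and PT counts of the maximum-severity summaries, including relationship by maximum severity. Show a subject with no graded event in the term under a 'Missing' severity row or column. This agrees with SAP 12.2 and with Protocol 9.8.
- **SAP 4.2.2:** for severity, refer to that display rule rather than to an imputation. The reference for relationship can stay.

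Settle the wording before unblinding, so that the choice cannot depend on which arm has ungraded events. The cost is a sentence or two in the SAP and one extra row or column in the table shells, which will be empty if every event is graded. Data collection does not change.

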9.2 Laboratory Evaluations

Data for the following hematology, serum chemistry, urinalysis, serology, lipid profile and coagulation analytes received from central laboratory and recorded in the eCRF are to be measured at the scheduled visits indicated in the study flowchart (Table 5).

[figure not shown]
Table 5: Laboratory Tests

Hematology Test (SI unit)	Serum Chemistry Test (SI unit)	Urinalysis (dipstick)
Hemoglobin (g/L) Hematocrit (%) WBC Count (10 ⁹ /L) Differential WBC (10 ⁹ /L and %) Neutrophils Lymphocytes Eosinophils Basophils Monocytes Platelet count (10 ⁹ /L)	Sodium (mmol/L) Potassium (mmol/L) Chloride (mmol/L) CO ₂ (mmol/L) Glucose (mmol/L) BUN (mmol/L) Creatinine (mmol/L) Calcium (mmol/L) ALT (U/L) AST (U/L) Total bilirubin (mmol/L) Total protein (g/L) Amylase (U/L) Lipase (U/L) Lipase (U/L)	pH Specific Gravity Protein Glucose Ketones Bilirubin Urobilinogen Blood Nitrite Leukocyte esterase Microscopic examination of the sediment only if abnormality seen on routine tests
Serology	Lipid Profile (SI unit)	Coagulation
 HIV-1/2 Antigen/Antibody Hepatitis panel Hepatitis B Virus Surface Antigen Hepatitis C Virus Antibody 	Total Cholesterol (mmol/L) HDL (mmol/L) LDL (mmol/L) Triglycerides (mmol/L)	Prothrombin Intl. Normalized Ratio Activated Partial Thromboplastin Time

SI = International System of Units; WBC = White Blood Cell; CO₂ = Carbon Dioxide; BUN = Blood Urea Nitrogen; ALT = Alanine Aminotransferase; AST = Aspartate Aminotransferase; HIV = Human Immunodeficiency Virus; HDL = High Density Lipoprotein; LDL = Low Density Lipoprotein.

Central laboratory data will be summarized by analysis visit (as defined in and) using default descriptive summary statistics for continuous variables for Parts 1 and 2 of the study separately, by treatment group and overall. Changes from Baseline will also be summarized.

For summaries which present the worst value with respect to the reference range at the subject level, low and high are each chosen in preference to normal values. For parameters with both lower and upper limits of the reference range, subjects who have assessments within both low and high ranges will be counted within each category for worst value summary tables.

The number and percentage of subjects with worst post-baseline categorized (low, normal and high) values relative to the reference range will be summarized for Parts 1 and 2 of the study separately, by laboratory analyte, treatment group and overall.

Listings of all clinical laboratory data including derived change from Baseline and listings of clinically significantly abnormal values will be provided for Parts 1 and 2 of the study separately.

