K0706 is a BCR-ABL tyrosine kinase inhibitor with limited off-target effects. Based on its mechanism of action and the results of the pre-clinical toxicology studies, the anticipated potential toxicities in humans with K0706 include K0706 is a teratogen, as are other BCR-ABL tyrosine kinase inhibitors, in view of the role of ABL signaling in embryo-fetal development. Otherwise, non-clinical toxicology studies with K0706 demonstrate a safety profile that supports administration to human subjects. In healthy controls, K0706 has been studied Potentially-related TEAEs were mild and typically caused In Parkinson's subjects, K0706 has been studied up to . TEAEs were typically and typically across subjects. is a common TEAE with other ABL inhibitors and is typically managed with stopping the treatment and often does not recur with restarting of the medication). . In the Ph+ CML study population enrolled in , in the emerging clinical data, the most commonly observed TEAEs included the following:

Additionally, certain class effects are known with the clinical use of BCR-ABL tyrosine kinase inhibitors such as Imatinib mesylate, Dasatinib, Nilotinib, and Ponatinib in the treatment of Philadelphia-positive leukemia. While some of the observed AEs are common between the BCRABL tyrosine kinase inhibitors and contribute as a class effect, specific adverse reactions are associated with the structure of the BCRABL tyrosine kinase inhibitors and are unique for the particular TKI (e.g.: Thromboembolic episodes in patients treated with Ponatinib). Since K0706 is being developed as a tyrosine kinase inhibitor for the treatment of Philadelphia-positive leukemia, AEs commonly observed with the approved BCRABL tyrosine kinase inhibitors class of drugs may be observed with the clinical use of K0706. The following AEs have been reported

during clinical studies and clinical use of BCR-ABL TKIs such as imatinib, dasatinib, nilotinib, ponatinib, and bosutinib:

- Fluid retention: It is advised to monitor subjects for the development of signs and symptoms of fluid retention
- Myelosuppression: It is advised to monitor complete blood counts regularly
- Cardiac arrhythmias: Subjects should be advised to report signs and symptoms of slow or rapid heart rate.
- Hepatic impairment: Caution is recommended in subjects with hepatic impairment
- Heart failure: Subjects should be monitored for signs or symptoms consistent with cardiac dysfunction and should be treated appropriately

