- Hepatotoxicity: It is advised to monitor liver function tests regularly
- Pancreatitis: Caution is recommended in subjects with a history of pancreatitis
- Hemorrhage: Caution is indicated in subjects requiring medications that inhibit platelet function or anticoagulants
- Pregnancy: Women should be advised of the potential hazard to the fetus and to avoid becoming pregnant
- Compromised wound healing and gastrointestinal perforation

Nilotinib is approved for CML at doses up to 1200 mg daily (European Union) and up to 800 mg daily (United States of America), where it carries a black box warning for QT interval prolongation. Sudden cardiac death and electrolyte disturbances have been reported in patients taking nilotinib, and it can also cause myelosuppression. In non-clinical studies of nilotinib, potentially pro-arrhythmic effects as evidenced by inhibition of hERG current, prolongation of action potential duration, and induction of triangulation and beat-to-beat variability in the in-vitro assay systems were observed

n-vitro assay	y systems we	re observed			
-					
	 				
			 _	1 4: - : 4	

Ponatinib use is associated with hepatic impairment, neuropathy, ocular toxicity, and vascular occlusion (arterial and venous)

There has been one open-label trial of nilotinib of five subjects with Dementia with Lewy Bodies (a similar condition to PD with early cognitive impairment) and 7 subjects with mid to late-stage PD (all but one with cognitive impairment) SAEs in that study included myocardial infarction, hospitalization for urinary tract infection, and hospitalization for pneumonia. All other side effects were considered mild. Of note, most participants experienced increased psychotic symptoms and dyskinesias, which the authors noted suggested a symptomatic benefit of nilotinib (i.e., increased dopamine levels).

Regarding potential benefits, non-clinical evidence of efficacy in animal models of PD is described in section 2.2.3. There have been no studies in humans regarding the effectiveness of K0706 on Parkinson's disease.

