6.4.2 Use of Anti-clotting Agents

Serious bleeding events, including fatalities, have occurred in patients treated with K0706 in (section 2.2.5), as well as other Abl TKIs used for leukemia. Cerebral hemorrhage and gastrointestinal hemorrhage were the most commonly reported serious bleeding events in studies of other Abl tyrosine kinase inhibitors, with most hemorrhagic events occurring in patients with Grade 4 thrombocytopenia. Most likely, the cause of bleeding in these subjects was disease progression, but until further information is available, caution is indicated in patients requiring medications that inhibit platelet function or anticoagulants.

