8.1.2 Clinical Laboratory Testing

The following tests will be performed by a central laboratory:

Hematology

- Hemoglobin, hematocrit
- Total WBC count
- Automated differential WBC count with reflex to manual differential if abnormality seen
- Platelet count

Chemistry

- Sodium
- Potassium
- Chloride
- CO₂
- Glucose
- Blood Urea Nitrogen (BUN)
- Creatinine
- Calcium
- Alanine Aminotransferase (ALT)
- Aspartate Aminotransferase (AST)
- Alkaline phosphatase
- Total bilirubin

- Total protein
- Albumin
- Amylase
- Lipase

Lipid Profile

- Total Cholesterol
- High-Density Lipoprotein (HDL)
- Low-Density Lipoprotein (LDL)
- Triglyceride

Urinalysis

- Routine testing, including dipstick for pH, specific gravity, protein, glucose, ketones, bilirubin, urobilinogen, blood, nitrite, leukocyte esterase
- Microscopic examination of the sediment only if abnormality seen on routine tests

Serology

• HIV, hepatitis panel

Results for clinical laboratory parameters will be evaluated for clinically significant values according to pre-specified criteria. Laboratory tests may also be repeated between scheduled visits at the discretion of the Investigator. In addition, repeat testing should be performed at the end of the study to follow any clinically significant abnormality to resolution/stabilization. Clinically significant results will be reported as AEs.

8.1.3 12-Lead ECG

12-lead ECG measurements will be collected in triplicate in a supine position after 5 minutes of rest. Within the triplicate series, ECGs are to be spaced no more than 2 minutes apart. The QTc data will be corrected using Fridericia's correction. In addition to the QT interval, the following parameters will be collected: PR interval, QRS, and ventricular rate, the presence of T-waves.

Clinically significant abnormalities will be reported as AEs.

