9.8.2 Clinical Laboratory Evaluation, Vital Signs Analysis, and ECG

Individual data for clinical laboratory, vital signs, and ECG parameters will be presented in tabular form with descriptive statistics, including the number of observations, arithmetic mean, median, standard deviation, and range (minimum and maximum) as appropriate. The data will be summarized by treatment groups and scheduled visits. For the laboratory safety data, out-of-range values will be flagged in the data listings, and a list of clinically significantly abnormal values will be presented. Individual results will be reviewed for any treatment-emergent changes of possible clinical significance.

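### SAP 9.2's only categorical laboratory table is worst low/normal/high, ungraded and not crossed with baseline, so no table counts marked liver, pancreatic or blood-count abnormalities by arm

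*SAP*

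**What the plan says.** SAP 9.2 plans three kinds of laboratory output.

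- **Continuous summaries** by analysis visit, "using default descriptive summary statistics for continuous variables for Parts 1 and 2 of the study separately, by treatment group and overall". It adds: "Changes from Baseline will also be summarized". Under SAP 12.2 the default statistics include the minimum and maximum.
- **One categorical table**, by analyte and treatment group: "The number and percentage of subjects with worst post-baseline categorized (low, normal and high) values relative to the reference range will be summarized". Low and high each outrank normal; distance beyond the limit plays no part.
- **Listings** of all results with change from baseline, and of clinically significant abnormal values.

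Protocol 8.1.2 says: "Results for clinical laboratory parameters will be evaluated for clinically significant values according to pre-specified criteria". It also has clinically significant results reported as adverse events. Protocol 9.8.2 adds: "Individual results will be reviewed for any treatment-emergent changes of possible clinical significance". The readable text gives no cut-offs for either step.

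Protocol 2.2.6 lists reactions seen with drugs of this class, among them "Hepatotoxicity: It is advised to monitor liver function tests regularly" and "Myelosuppression: It is advised to monitor complete blood counts regularly", and also pancreatitis. Safety and tolerability is a secondary objective of Part 1 (Protocol 3.1.2) and the primary objective of Part 2 (Protocol 3.2.1).

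**The concern.** The categorical table is the only planned display that counts subjects with abnormal laboratory values by arm, and it blurs two distinctions.

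**Size.** An ALT slightly above the upper limit and one many times above it fall in the same cell. For drug-induced liver, pancreatic or marrow effects the informative cases are the few marked ones, and here they are pooled with marginal values. Nothing counts subjects with raised aminotransferases and raised bilirubin together.

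**Onset.** The worst post-baseline category is not crossed with the baseline category, so abnormality present at entry cannot be told from abnormality that arose on treatment. Part 2 is affected most: its baseline is generally the Week 40 value (SAP 4.1.2), by which time subjects from the two active arms have been on drug for 40 weeks.

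At stake is how readily a reader of the tables could see that a dose produces a small excess of marked abnormalities. The primary efficacy result is not affected.

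**Working it through.** The plan states no figure on this point, so there is none to reproduce. The check has two parts.

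**1. What each planned output shows about marked abnormalities**

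| Output | Shows marked cases? | Counts subjects by arm and analyte, by size? |
|---|---|---|
| Low/normal/high table (SAP 9.2) | Only inside any-high or any-low | No |
| Continuous summaries (SAP 9.2, 12.2) | Visit extreme only | No |
| Listings (SAP 9.2) | Yes, one by one | No; hand count |
| TEAE tables (SAP 9.1) | If judged clinically significant | No; by coded term, severity by tolerability |
| *For comparison:* QTcF (SAP 9.4) | Yes | Yes; bands for value and for change |
| *For comparison:* blood pressure and pulse (SAP 9.3) | Yes | Worst investigator assessment, including clinically significant |

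In Protocol 8.5, severity depends on how well the event is tolerated and whether it disturbs daily activity. An asymptomatic but large enzyme rise can therefore be rated mild, and the maximum-severity table does not stand in for grading.

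Under SAP 4.1.4 unscheduled results enter the visit windows, but a scheduled result takes precedence within a window. SAP 9.2 does not say whether the worst value is taken before or after that selection. Protocol 8.1.2 lets investigators repeat tests between visits, and such a repeat may catch a peak.

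**2. Illustration of the dilution (all event rates are assumptions)**

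Inputs from the documents: 506 subjects planned and 1:1:1 allocation, so 506/3 = 168.7, about 169 per arm.

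Assumptions: background any-high rate b = 5% to 30%; excess e = 3% or 5% of one active arm with a marked elevation; background marked rate 0.3%; two-sided 5% level. The range for b is plausible. If 2.5% of normal results exceed the upper limit and visits were independent, the chance of at least one high in 8 visits is 1 − 0.975^8 = 18%. Correlation within subjects would lower this.

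Any-high rate on active: p₁ = b + (1 − b)e. Marked rate on active: 0.003 + e.

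Power = Φ[(d − 1.96·se₀)/se₁], where d is the rate difference, se₀ its pooled and se₁ its unpooled standard error.

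Example, b = 10% and e = 3%:
- p₁ = 0.10 + 0.90 × 0.03 = 0.127 and d = 0.027.
- se₀ = √(0.1135 × 0.8865 × 2/169) = 0.0345.
- se₁ = √[(0.10 × 0.90 + 0.127 × 0.873)/169] = 0.0345.
- Power = Φ[(0.027 − 0.0676)/0.0345] = Φ(−1.18) = 12%.

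| Row of table | Expected subjects, e = 3% | Power, e = 3% | Power, e = 5% |
|---|---|---|---|
| Any-high, b = 5% | 8.5 vs 13.3 | 19% | 39% |
| Any-high, b = 10% | 16.9 vs 21.5 | 12% | 24% |
| Any-high, b = 20% | 33.8 vs 37.9 | 8% | 14% |
| Any-high, b = 30% | 50.7 vs 54.2 | 6% | 10% |
| Marked only | 0.5 vs 5.6 | 55% | 80% |

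The normal approximation is rough when about 0.5 events are expected in one arm. Enumerating Fisher's exact test over both binomials gives 36% (e = 3%) and 78% (e = 5%) for the marked row, against 5.5% to 13% and 9% to 31% for the any-high row. The ordering stands.

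The mean is no better. If 3% of subjects rise by an assumed 100 U/L, the arm mean moves by 0.03 × 100 = 3 U/L.

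**The case against.** A reader might infer that the SAP reduces all laboratory data to three categories, that clinically significant values appear only in listings, or that a signal would be lost. The documents do not support any of these. SAP 9.2 also plans continuous summaries by arm with change from baseline, and an extreme ALT would appear as that visit's maximum unless it was an unscheduled result displaced by a scheduled one in the window. Clinically significant results become adverse events, and SAP 9.1 tabulates these by arm, severity, relationship, seriousness and discontinuation of treatment. Protocol 9.8.1 adds a summary by actual dose at onset. Protocol 8.7 provides roughly monthly safety review and, if triggered, a DSMB with unblinded data. Individual marked cases would therefore be found, and the tables by arm can show a dose pattern if investigators report the abnormalities.

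Two further objections carry weight. The cut-offs may exist in the pre-specified criteria, in the separate table shells that SAP 12.2 cites, or in text that cannot be read; SAP 9.2 itself shows no gap where a graded or shift table would stand. The numbers above are also illustrative and fragile: 5/169 against 0/169 gives Fisher p = 0.061, and a single placebo case moves it to 0.21. The case for grading is descriptive and does not rest on a significance test.

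Bleeding is a separate matter. Protocol 6.4.2 says "Serious bleeding events, including fatalities, have occurred in patients treated with K0706 in", where the sentence meets a gap, and the same paragraph considers disease progression the most likely cause. It supports a grouped table as an option, not a finding that the plan neglects a known K0706 effect in Parkinson's disease.

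What survives is narrower: extremes, listings and investigator-judged terms are not counts by arm of subjects with marked values, and nothing shows shift from baseline category.

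**Conclusion.** The concern holds in this limited form. The only categorical laboratory table in the readable SAP is worst low/normal/high, without grading, baseline cross-tabulation or a joint aminotransferase-bilirubin count. For the analytes tied to three named class risks, no output counts marked abnormalities by arm, while QTcF is graded. A small excess of marked cases would be diluted in the table and would have to be assembled from visit extremes, listings and adverse events. It would not be invisible.

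The absence of such tables is read directly from SAP 9.2, subject to what unseen criteria or shells may contain. The size of the dilution rests entirely on assumed rates. This is a cheap improvement to safety reporting; design, data collection and efficacy analyses are untouched.

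**What to change.** In SAP 9.2, for Parts 1 and 2:

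1. Add shift tables by arm and analyte of baseline category against worst post-baseline category, using each Part's own baseline.
2. Add counts and percentages by arm in pre-defined multiple-of-limit or graded bands for ALT, AST, bilirubin, amylase, lipase, platelets and neutrophils, with a joint aminotransferase-bilirubin count. State the pre-specified criteria of Protocol 8.1.2, or cite where they stand, and align the bands with them before unblinding.
3. State that the worst value is taken over all post-baseline results, including unscheduled ones that the visit-window rule does not select.

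Optionally, add to SAP 9.1 a descriptive table by arm of grouped haemorrhage terms, because tables by system organ class and preferred term do not sum bleeding across classes. The sentence in SAP 9.1 on statistical comparison of adverse events is incomplete in the readable text, so any interval or test should first be reconciled with its full wording.

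If the table shells already contain these displays, a cross-reference in SAP 9.2 is enough. Otherwise the cost is a short SAP edit and a few more tables to program and review, from central-laboratory and coded adverse-event data already collected.
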